9.2 Populations for Analyses

The intention-to-treat (ITT) population will be the basis for the primary analysis of efficacy in this study, and constitutes all randomized subjects. Subjects in the ITT population will be included in the treatment group to which they were randomized.

9.3 Demographics and Baseline Characteristics

Subject characteristics including demographics, baseline performance status, disease characteristics, and baseline laboratory parameters will be summarized by randomized treatment arm as well as pooled across randomized arms using descriptive statistics.

9.4 Primary Efficacy Analysis

The primary analysis of PFS, will be to compare the two randomized arms via a two-sided, log-rank test stratified by β_2 microglobulin levels ($<$ vs ≥ 3 mg/L), prior lines of anti-MM treatment (3 vs >3) and subjects' age (\leq vs >75 years).

Further analysis of PFS will include the computation of hazard ratios and estimation of PFS functions.

The PFS hazard ratio of Pom/dex to DEX will be computed using a stratified Cox proportional hazards model with treatment arm as the sole covariate. The PFS functions for each randomized arm will be estimated using the Kaplan-Meier product-limit method.

Two-sided, 95% confidence intervals for median PFS will be computed by randomized arm. PFS rates at 1, 2, 3, 6 and 12 months will be estimated from the Kaplan-Meier curve. Each analysis will be performed after all subjects had been followed for the given time point estimate (ie, the 2-month PFS rate estimate will be estimated when all subjects have been followed for a minimum of 2 months).

A total of 125 progression events will provide 90% power to detect, with a 1-sided significance level of 0.025, a 50% increase in median PFS for the Pom/dex arm vs the DEX arm (3 vs 2 months, respectively).

9.5 Secondary Efficacy Analysis

Survival will be compared between arms using a stratified group sequential log-rank test procedure. The stratification factors will be the same as those used for the analyses of PFS. The OS function for each randomized arm will be estimated using the Kaplan-Meier method. Two-sided, 95% confidence intervals for median OS will be computed by randomized arm. OS rates at 4, 6, 9 and 12 months will be

estimated from the Kaplan-Meier curve. Each analysis will be performed after all subjects had been followed for the given time point estimate (ie the 8-month OS rate estimate will be estimated when all subjects have been followed for a minimum of 8 months). The hazard ratio for treatment group will be estimated using a stratified Cox proportional hazards model.

9.6 Sub-group analysis

The effect of treatment on the key efficacy variables PFS and OS will be evaluated within subgroups such as:

- Region.
- Age (\leq vs >75 years).
- Gender
- ECOG performance status (0 vs 1 vs 2).
- baseline cytogenetic categories.
- Number of previous anti-MM therapies (3 vs >3).
- Prior ASCT

Additional multivariate analysis on PFS and OS will be carried out to evaluate the treatment effect while adjusting for the aforementioned factors (subgroups).

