1.2 Study design

This is a Phase 3, randomized, open-label, multicenter study comparing two treatment regimens for subjects with RRMM. Eligible subjects will be randomized in a 1:1 ratio to receive either the control DEX or Pom/dex. Randomization will be stratified by β_2 microglobulin levels ($<$ vs ≥ 3 mg/L), prior lines of anti-MM treatment (3 vs >3) and subjects' age (\leq vs >75 years). The primary endpoint of this Phase 3 study is progression-free survival. Subjects will receive the treatment determined by randomization in 28-day cycles until disease progression or unacceptable toxicity (whichever occurs first).

Long-term follow-up for disease status and survival will continue until the subject has withdrawn consent for further participation, is lost to follow-up, has died, or the Sponsor makes a decision to close the study.

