4.4 Subject enrollment and randomization

Each subject enrollment must be approved by the study sponsor or designee before randomization can take place (see separate study manual). Key eligibility criteria must be made available.

Randomization is recognized as an appropriate means to minimize bias in subject selection for efficacy assessment in clinical trials with 2 (or more) treatment arms. The randomization schedule will be prepared using a blocked randomization scheme. A unique subject number will be assigned at the time of randomization that will be used to identify the subject throughout the clinical study and must be used on all study documentation related to that subject.

To minimize potential imbalances between groups in subject characteristics that may influence the study results randomization will be stratified by $\beta 2$ microglobulin levels ($< vs \geq 3$ mg/L), prior lines of anti-MM treatment (3 vs >3) and subjects' age ($\leq vs >75$ years).

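### The adjusted PFS and OS models in section 9.6 take in two of the three randomization stratification factors but leave out beta-2 microglobulin

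*Protocol*

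**What the plan says.** **Randomization.** Protocol section 1.2 states: "Randomization will be stratified by β_2 microglobulin levels" (below 3 versus 3 mg/L or more), together with prior lines (3 versus more than 3) and age (75 years or younger versus older). Section 4.4 repeats the three factors and gives the reason: "To minimize potential imbalances between groups in subject characteristics that may influence the study results randomization will be stratified by" them.

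**Primary PFS analysis.** Section 9.4 will "compare the two randomized arms via a two-sided, log-rank test stratified by β_2 microglobulin levels", prior lines and age. The hazard ratio comes from a "stratified Cox proportional hazards model with treatment arm as the sole covariate".

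**OS analysis.** Section 9.5 uses a stratified log-rank procedure and a stratified Cox model. On the factors it says: "The stratification factors will be the same as those used for the analyses of PFS".

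**Subgroups and adjusted models.** Section 9.6 says: "The effect of treatment on the key efficacy variables PFS and OS will be evaluated within subgroups such as" the seven items that follow: region, age, gender, ECOG performance status, baseline cytogenetic category, "Number of previous anti-MM therapies (3 vs >3"), and prior ASCT. It then adds multivariate PFS and OS analyses, whose covariates are fixed only by reference back to that list: "to evaluate the treatment effect while adjusting for the aforementioned factors (subgroups").

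**The concern.** The protocol names three characteristics that may influence the results, and it carries all three from randomization into the main PFS and OS analyses. In section 9.6 two of them reappear at identical cuts. The third, which is named first elsewhere, does not, and no reason is given. This is more than a detail left for later, because the protocol does state an adjustment set and that set sits awkwardly with its own choice of influential factors.

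What is at stake is how the supportive analysis reads. The Cox hazard ratio is non-collapsible: leaving out a prognostic covariate moves the treatment hazard ratio toward 1 even when the arms are perfectly balanced on it. A multivariate model that lacks a known stratification factor is therefore a slightly weaker companion to the stratified result. In an open-label trial it is also better to fix the covariates beforehand than to add one after results are seen.

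**Working it through.** The point rests on comparing factor lists. The protocol gives no figure to reproduce.

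**Step 1. Set the lists side by side.**

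| Place in protocol | Beta-2 microglobulin | Prior lines (3 vs >3) | Age (≤75 vs >75) |
|---|---|---|---|
| 1.2 and 4.4, randomization | yes | yes | yes |
| 9.4, PFS log-rank test | yes | yes | yes |
| 9.5, OS log-rank test (same factors as PFS) | yes | yes | yes |
| 9.6, subgroup list | **no** | yes | yes |
| 9.6, multivariate PFS and OS models (factors of that list) | **no** | yes | yes |

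So 2 of the 3 stratification factors are in section 9.6. No other section adds the third to the multivariate models.

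**Step 2. Could the multivariate models be stratified without saying so?** Sections 9.4 and 9.5 describe their Cox models as stratified; section 9.6 does not. If the section 9.6 models were stratified by all three factors, age and prior lines would be both strata and covariates at the same cuts. Each would then be constant within every stratum, and its coefficient could not be estimated. Listing them as adjustment factors fits an unstratified model better, but the text does not settle it.

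**Step 3. Size of the effect, as an illustration.**

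- From the protocol: control median PFS 2 months and Pom/dex median 3 months, so a hazard ratio of 2/3 = 0.667; 125 progression events; 250 subjects.
- Assumed, not in the protocol: the share of subjects at 3 mg/L or above, and the prognostic hazard ratio of that group.

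Cox fits to 40,000 simulated subjects, 50% in the high group, true treatment hazard ratio 0.667:

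| Assumed prognostic HR | Treatment HR, factor omitted | Shift, ln(HR/0.667) |
|---|---|---|
| 1.5 | 0.677 | 0.015 |
| 2.0 | 0.686 | 0.028 |
| 2.5 | 0.706 | 0.057 |

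With the factor included, the same fits gave 0.663 to 0.670.

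A second, separate simulation used exponential PFS times, uniform censoring over 0 to 12 months and 20,000 subjects per scenario. The standard error of the simulated log hazard ratio was about 0.016:

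| Assumed prognostic HR | Share high | HR, factor omitted | HR, stratified by it |
|---|---|---|---|
| 1.0 | 50% / 70% | 0.659 / 0.667 | 0.659 / 0.667 |
| 1.5 | 50% / 70% | 0.683 / 0.674 | 0.670 / 0.668 |
| 2.0 | 50% / 70% | 0.682 / 0.676 | 0.656 / 0.654 |
| 3.0 | 50% / 70% | 0.695 / 0.724 | 0.653 / 0.665 |

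A non-prognostic factor (1.0) gives no shift, as it should. Otherwise the direction is always toward 1. Simulation noise makes the second decimal approximate.

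**Step 4. Compare with sampling error.** With 1:1 allocation, SE(log HR) ≈ 2/√events.

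- At 125 events: 2/√125 = 0.179. The 95% interval around 0.667 is exp(ln 0.667 ± 1.96 × 0.179), about 0.47 to 0.95. The shifts are 0.015/0.179 = 0.08, 0.028/0.179 = 0.16 and 0.057/0.179 = 0.32 standard errors.
- If all 250 subjects had an event: 2/√250 = 0.126, and the same shifts are about 0.12, 0.22 and 0.45 standard errors.
- At the extreme assumed (prognostic hazard ratio 3, 70% high): ln(0.724/0.667) = 0.082, or 0.082/0.179 = 0.46 standard errors at 125 events.

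**The case against.** The case against has real weight.

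- **The subgroup list is open.** It is introduced as examples, so a beta-2 microglobulin subgroup is allowed though not named. A reader might infer that the plan rules out checking the effect in the low and high groups; the text does not support that. The openness helps the covariate set less: that set is defined by the factors mentioned, and beta-2 microglobulin is not one of them.
- **Final covariate lists often belong in the SAP.** That would dispose of the point had the protocol left the set blank. It states one instead, and the remark concerns what is stated.
- **The models might be stratified.** This cannot be excluded, and if they are, the factor is accounted for. Step 2 shows why the text reads more naturally the other way.
- **The main inference already handles the factor.** This stands in full. A reader might infer that the PFS or OS comparison ignores beta-2 microglobulin; sections 9.4 and 9.5 show otherwise. The type I error and power of the primary test are untouched.
- **Disagreement with the primary hazard ratio cannot be pinned on this factor.** This also stands. The section 9.6 models adjust for region, gender, ECOG, cytogenetics and prior ASCT, none of which is a stratum in section 9.4. The two hazard ratios condition on different things and could differ even after the fix.
- **The size is an illustration.** The simulations contain treatment and one binary factor. In the planned model, ECOG, cytogenetics, age and prior lines may already carry part of any beta-2 microglobulin effect, so the shift could be smaller.

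**Conclusion.** The point holds in a limited form. By its own wording, section 9.6 builds the multivariate PFS and OS models from a list with two of the three stratification factors, omits beta-2 microglobulin, and does not say that the models are stratified. This is an internal inconsistency in a supportive analysis; it does not threaten the trial's main conclusions.

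If the factor is prognostic, the adjusted hazard ratio would be drawn modestly toward 1: from 0.667 to about 0.68 to 0.71 for assumed prognostic hazard ratios of 1.5 to 2.5 with half the subjects in the high group. The direction follows from the model. The amount depends on prevalence and prognostic strength, which the protocol does not give, and it is small beside the sampling error at 125 events. The change is worth making because it costs nothing.

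**What to change.** Add one line to the list in section 9.6: beta-2 microglobulin, <3 versus ≥3 mg/L. It then becomes both a named subgroup and a covariate in the multivariate PFS and OS models, at the randomization cut.

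Alternatively, state in section 9.6 that the multivariate models are stratified by beta-2 microglobulin, with age and prior lines kept as covariates and not also used as strata. This settles the adjusted models but does not name the subgroup.

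The cost is one line of text. The value must be known for every subject before stratified randomization, so no new data are needed, and sample size and the primary test stay the same.

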10. STUDY MANAGEMENT

10.1 Monitoring

Monitoring visits to the trial site will be made periodically during the trial, to ensure that all aspects of the protocol are followed. Source documents will be reviewed for verification of agreement with data on CRFs. The investigator/institution guarantees direct access to source documents by the Sponsor and appropriate regulatory agencies.

The trial site may also be audited (quality assurance) by the Sponsor as well as inspected by appropriate regulatory agencies.

It is important that the investigator and their relevant personnel area are available during the monitoring visits and possible audits and that sufficient time are devoted to the process.

10.2 Investigational Site Training

The Sponsor will provide quality investigational staff training prior to study initiation. Training topics will include but are not limited to: GCP, AE reporting, study details and procedure, electronic CRFs, study documentation, informed consent.

10.3 Source documents

Source records are original documents, data, and records (eg, medical records, raw data collection forms, pharmacy dispensing records, recorded data from automated instruments, laboratory data) that are relevant to the clinical study. The Investigator will prepare and maintain adequate and accurate source documents. These

documents are designed to record all observations and other pertinent data for each subject enrolled in this clinical study. Source records must be adequate to reconstruct all data entered into the CRFs. Case report forms will be completed in English.

10.4 Case Report Forms

As part of the responsibilities assumed by participating in the study, the Investigator agrees to maintain adequate case histories for the subjects treated as part of the research under this protocol. The Investigator agrees to maintain accurate electronic CRFs (eCRFs) and source documentation as part of the case histories. These source documents may include subject diaries, laboratory reports, etc. The Sponsor will supply the eCRF, which will be completed in English.

10.5 Data Retention

The investigator must retain all study records and source documents for the maximum period required by applicable regulations and guidelines, or institution procedures, or for the period specified by the Sponsor, whichever is longer. The investigator must contact the Sponsor prior to destroying any records associated with the study. The Sponsor will notify the investigator when the study records are no longer needed. If the investigator withdraws from the study (eg, relocation, retirement), the records shall be transferred to a mutually agreed upon designee (eg, another investigator, IRB). Notice of such transfer will be given in writing to the Sponsor.

10.6 Data quality assurance

The clinical research associates will visit each study site, at a frequency documented in the monitoring plan, to review (e)CRFs for completeness and accuracy. Any discrepancies found between source documents and completed CRFs will be entered as a discrepancy in the EDC system by the clinical research associate, which will then be addressed by the study site personnel. Uniform procedures for CRF correction (queries) will be discussed at the Investigator meeting, during the study site initiation visits, and will be documented in the study operations manual.

Data from CRFs and other external data sources will be entered into a clinical database as specified in the data management plan. Quality control and data validation procedures will be applied to ensure the validity and accuracy of the clinical database.

10.7 Data Monitoring Committee

A data monitoring committee (DMC) will be charged with monitoring safety and trial conduct throughout the course of this study. The DMC will also review the final efficacy analysis of PFS.

11. REGULATORY OBLIGATIONS

11.1 Compliance with Good Clinical Practice, Laws and Regulations

This Trial Protocol is designed to comply with the Guideline produced by the International Conference on Harmonization (ICH) on the topic Good Clinical Practice (GCP-E6) and published by the European Agency for the Evaluation of Medicinal Products as “Note for Guidance on Good Clinical Practice” (CPMP/ICH/135/95) and in accordance with the general ethical principles outlines in the Declaration of Helsinki. The Investigator will conduct all aspects of this study in accordance with applicable national and local laws of the pertinent regulatory authorities. The study will receive approval from an IRB/IEC prior to commencement.

11.2 Compliance with the Protocol and Protocol Revisions

The study shall be conducted as described in this approved protocol. All revisions to the protocol must be discussed with, and be prepared by the Sponsor. The investigator should not implement any deviation or change to the protocol without prior review and documented approval/favorable opinion from the IRB/IEC of an amendment, except where necessary to eliminate an immediate hazard(s) to study subjects. Any significant deviation must be documented in the CRF. If a deviation or change to a protocol is implemented to eliminate an immediate hazard(s) prior to obtaining IRB/IEC approval/favorable opinion, as soon as possible the deviation or change will be submitted to:

- IRB/IEC for review and approval/favorable opinion
- the Sponsor
- Regulatory Authority(ies), if required by local regulations.

Documentation of approval signed by the chairperson or designee of the RB(s)/IEC(s) must be sent to the Sponsor.

If an amendment substantially alters the study design or increases the potential risk to the subject:

- (1) the consent form must be revised and submitted to the IRB(s)/IEC(s) for review and approval/favorable opinion;
- (2) the revised form must be used to obtain consent from subjects currently enrolled in the study if they are affected by the amendment; and
- (3) the new form must be used to obtain consent from new subjects prior to enrollment.

If the revision is an administrative letter, investigators must inform their IRB(s)/IEC(s).

11.3 Institutional Review Board/Independent Ethics Committee review and approval

Before the initiation of the study, the protocol, the informed consent document and any other appropriate documents will be submitted to the IRB/IEC for approval. If applicable the same documents will also be submitted to the authorities in accordance to legal requirements.

Only after the sponsor receives the approval, can the investigational drug be supplied to a study site. The formal approval by the IRB/IEC should mention the

protocol title, number, amendment number, study site and any other documents reviewed. It must mention the date of the approval decision and signed by a Committee member.

12. COMMUNICATION OF RESULTS AND PUBLICATION POLICY

12.1 Use of Information

All unpublished information relating to this trial and/or to the trial drug is considered confidential by the sponsor and shall remain the sole property of the sponsor. The investigator must accept that the Sponsor may use the information from this clinical trial in connection with the development of the product, and therefore, may disclose it as required to other investigators, to government licensing authorities, to regulatory agencies of other government, stock exchange market, and commercial partners.

12.2 Publication

The Sponsor acknowledges the investigators right to publish the entire results of the trial, regardless of the outcome.

The International Coordinating Investigator will together with the Sponsor decide on the publication strategy and has the right to publish and present the results and methods as first author of multicenter publications. Co-authorship will be decided by the Sponsor and International Coordinating Investigator and will be limited to a number of persons, who have contributed substantially in the conduct of the trial.

The Sponsor will have representation in the list of authors.

Publications are subject to the following conditions:

- No publication prior to the completion of the trial at all participating sites without written approval from the Sponsor.
- All proposed publications and presentations, including any modifications or amendments shall be submitted to the Sponsor for its review at least 30 days before such presentation or publication is submitted to any third party.
- Publications shall not disclose any Sponsor Confidential Information and Property (not including the trial results, which can be published as described elsewhere in this section).

14. LIST OF ABBREVIATIONS

AE: Adverse Event
 ASCT: Autologous Stem Cell Transplantation
 CBC: complete blood count
 CR: Complete Response
 (e)CRF: (electronic) Case Report Form
 dex: Low-dose dexamethasone
 DEX: High-dose dexamethasone
 DLT: Dose-Limiting Toxicity
 DMC: Data Monitoring Committee
 EBMT: European Group for Blood and Marrow Transplantation
 ECOG: Eastern Cooperative Oncology Group
 EDC: Electronic Data Capture
 ICF: Informed consent Form
 IMiDS: Immunomodulatory Drugs
 IMWG: International Myeloma Working Group
 IND: Investigational New Drug
 I(M)P: Investigational (Medicinal) Product
 IEC: Independent Ethics Committee
 IRB: Institutional Review Board
 IRC: Independent Review Committee
 ITT: Intention To Treat
 IV: Intravenous
 LTFU: Long-Term Follow-Up
 (s)MM: (symptomatic) Multiple Myeloma
 MP: Melphalan/Prednisolon
 MR: Marginal Response
 OS: Overall Survival

[name], 2015

PD: Progressive Disease
PFS: Progression Free Survival
PO: Per Os
Pom: Pomalidomide
Pom/dex: Pomalidomide in combination with low-dose dexamethasone
PR: Partial Response
RRMM: Relapsed and/or Refractory Multiple Myeloma
SAE: Serious Adverse Event
SPEP: Serum Protein ElectroPhoresis
UPEP: Urine Protein ElectroPhoresis
VGPR: Very Good Partial Response
